#### **2.4.4 Analyses of efficacy endpoints**

All primary, secondary and exploratory analyses of efficacy endpoints will be performed using the all treated/safety population.

##### ***2.4.4.1 Analysis of primary efficacy endpoint***

The primary analysis is based on the dose level determined as MTD combined in phase 1 and phase 2. ORR as assessed by IAC will be summarized. The null hypothesis that the true response rate (ORR) is <10% will be tested using a one-sided exact binomial test with a significance level of 0.025. A 95% two-sided confidence interval will be computed for ORR using Clopper-Pearson method.

##### ***2.4.4.2 Analyses of secondary efficacy endpoints***

The following analyses will be performed.

- A 95% two-sided confidence interval will be computed for CBR using Clopper-Pearson method.
- OS and PFS will be analyzed by using the Kaplan-Meier method. The Kaplan-Meier estimates of the 25th, 50th and 75th percentiles and probability of surviving at every 4

months and the corresponding 95% confidence interval will also be computed. The Kaplan-Meier curves will be plotted.

- DOR and TTR will be summarized with descriptive statistics for patients who achieve a response  $\geq$  PR.
- DFU will be summarized with descriptive statistics.
- Paraprotein, the change and the percent change from baseline will be summarized with descriptive statistics for each cycle. Best percent change in paraprotein will be displayed in a waterfall plot. In the waterfall plot, patients with BOR of  $\geq$  PR will have negative percentage change. The patients will be ordered from highest positive change to smallest negative change. Percent change  $>100\%$  will be displayed as 100% increases.
- A swimmer plot of time on a treatment and a waterfall plot of best percent change in paraprotein will be provided. The patients will be ordered by BOR and duration of exposure. Patients with the best BOR and longest duration will be presented at the top of the plot.

A listing of best percent change in % plasma cell in bone marrow biopsy will be provided and will include the following variables: measurable paraprotein at baseline, best percent change in paraprotein, BOR, baseline plasma cells count and post baseline plasma cells count (only for CR confirmation) and best percent change in plasma cells count.

A listing of MRD negative patients will be provided (if any).

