--	---

	
Pharmacokinetics parameters will be summarized with descriptive statistics (mean, geometric mean, median, standard deviation, coefficient of variation, minimum and maximum).
 
Immune response, pharmacodynamics marker results will be descriptively summarized and tabulated.
 
Analysis of efficacy endpoints:
 
Best overall response will be listed along with relevant patient/disease characteristics as well as the secondary efficacy endpoints.
 
Primary analysis:
 
Analysis of efficacy endpoint will be performed on all patients who received at least one of the recommended dose across Phase I and II part:
 
ORR and a 95% two-sided confidence interval will be computed using Clopper-Pearson method. For recommended dose level, the null hypothesis that the true response rate (ORR) is <10% will be tested using a one-sided exact binomial test with a significance level of 0.025.
 
Secondary analysis:
 
The CBR will be analyzed using the same method as the primary efficacy analysis of ORR.
 
DOR, TTP, PFS and OS will be analyzed using Kaplan-Meier methods.
 
Analysis of the other exploratory endpoints:
 
The same analysis will be applied in Phase I and Phase II part.
 
The exploratory endpoints and the relationship to clinical outcomes will be analyzed with exploratory manner.
 
Planned database lock date:
 
The first cutoff date for the database lock is planned at approximately 4 months after last patient first dosed.
 
The second cutoff date for the database lock is planned at approximately 20 months after last patient first dosed.

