6.7.2 Determination of End of Clinical Trial (all patients)

The first analysis cutoff date for the statistical analysis for ORR will be 4 months after the date of the first dose of the last patient.

Second analysis cutoff date for the updated analysis of ORR and final analysis of time to events data will be 20 months after the date of the first dose of the last patient. Patients still on treatment at time of the second analysis cutoff date and who still continue benefiting from treatment with isatuximab will have the option to continue treatment under this protocol. Study will end after the completion of follow-up for all patients.

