13.4.8.3 Analysis of secondary efficacy endpoint for Phase II part of the study

The CBR will be analyzed using the same method as the primary efficacy analysis of ORR. The DOR, TTP, PFS and OS will be analyzed using the Kaplan-Meier method. The Kaplan-Meier estimates of the 25th, 50th and 75th percentiles and the 95% confidence intervals will also be computed. The Kaplan-Meier curves will be plotted.

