#### **2.1.3.2 Secondary efficacy endpoint(s)**

Secondary efficacy endpoints are defined below.

- Duration of Response (DOR) (in weeks): DOR is defined as the time from the date of the first IAC determined response ( $\geq$  PR) that is subsequently confirmed, to the date of first IAC determined PD or death, whichever happens earlier (if reported before the analysis cut-off date or the date of initiation of a new anticancer treatment). If progression and death are not observed before the analysis cut-off date or the date of initiation of new anticancer treatment, DOR will be censored at the earliest of the date of the last valid disease assessment not showing disease progression performed prior to initiation of a further anticancer treatment or the analysis cut-off date. DOR is determined only for patients who have achieved a confirmed response of  $\geq$ PR.
- Clinical benefit rate (CBR): defined as the proportion of patients with sCR, CR, VGPR, PR or MR as BOR according to IMWG criteria, as determined by the IAC.
- Progression free survival (PFS) (in months): defined as the time interval from the date of first isatuximab administration to the date of the first IAC-confirmed disease progression or the date of death due to any cause, whichever comes first. For patients who did not experience IAC-confirmed disease progression and death before the analysis cut-off date or the date of initiation of new anticancer treatment, PFS will be censored at the date of the last valid disease assessment not showing disease progression performed prior to initiation of a further anticancer treatment or the analysis cut-off date, whichever comes first.
- Overall survival (OS) (in months): defined as the time interval from the date of first isatuximab administration to death from any cause. In the absence of the confirmation of death before the cut-off date, OS will be censored at the cut-off date or at the last date the patient is known to be alive, whichever comes first.

- Time to response (TTR) (in weeks): TTR is defined as the time from first dose to first IAC response (PR or better) that is subsequently confirmed.
- Duration of follow-up (DFU) (in weeks): DFU is defined as the time from first dose to last response disease assessment before start of other therapy or cut-off date, whichever comes first.

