## **2.4 STATISTICAL METHODS**

### **2.4.1 Demographics and baseline characteristics**

Continuous data will be summarized using the number of available data, mean, standard deviation, median, minimum, and maximum for each treatment group. Categorical and ordinal data will be summarized using the number and percentage of patients.

Parameters described in [Section 2.1.1](#) will be summarized using descriptive statistics.

Past medical or surgical history other than multiple myeloma will be summarized by SOC (sorted by internationally agreed order) and PT (sorted by alphabetical order) for the all treated population.

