## 4 DATABASE LOCK

The database lock is planned to be twice in phase 2. The cut off for the first database lock is at approximately 4 months after last patient first dosed. The cut off for the second database lock is at approximately 12 months after last patient first dosed.

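### The Phase 2 SAP summarises censored duration of response with plain descriptive statistics and leaves out time to progression, although the protocol requires Kaplan-Meier for both

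*SAP*

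**What the plan says.** Protocol 13.4.8.3, on secondary efficacy in the Phase II part, states: "The DOR, TTP, PFS and OS will be analyzed using the Kaplan-Meier method". It adds: "The Kaplan-Meier estimates of the 25th, 50th and 75th percentiles and the 95% confidence intervals will also be computed". It also asks for the curves. The secondary analysis paragraph of the Clinical Trial Summary agrees: "DOR, TTP, PFS and OS will be analyzed using Kaplan-Meier methods". Protocol 9.3.1 defines both DOR and TTP with censoring rules, and the Clinical Trial Summary lists both among the efficacy parameters.

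Phase 2 SAP 2.1.3.2 also censors DOR. For a responder with neither progression nor death, "DOR will be censored at the earliest of the date of the last valid disease assessment not showing disease progression" or the analysis cutoff. SAP 2.4.4.2 then gives Kaplan-Meier to OS and PFS and, in a separate bullet, says that "DOR and TTR will be summarized with descriptive statistics for patients who achieve a response" of PR or better.

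TTP is absent from the SAP's secondary endpoints (2.1.3.2), its analyses (2.4.4.2) and its abbreviation list. Table 1 in SAP 1.5 records three Amendment 1 changes, none on DOR or TTP, and SAP 1.6 records no modifications.

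**The concern.** A variable with a censoring rule needs a method that uses the censoring indicator, and a plain summary has no place for it. TTR, which shares the bullet with DOR, is different: in responders it is always fully observed, so descriptive statistics suit it. DOR is not always fully observed.

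Two things are at stake. For DOR, the documents prescribe different methods, so the analyst must choose between them. If the SAP is followed, ongoing responses enter as completed ones, and the quartiles, confidence intervals and curve are not produced. For TTP, an endpoint with a specified analysis in the protocol has no planned output. DOR shows how long the responses counted in the primary ORR last, so how it is reported matters even though it is not tested.

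**Working it through.** **Text comparison**

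| Item | Protocol | Phase 2 SAP |
|---|---|---|
| DOR definition | 9.3.1, censored | 2.1.3.2, censored |
| DOR analysis | Kaplan-Meier, quartiles, 95% CIs, curve | descriptive statistics |
| TTP definition | 9.3.1, censored | none |
| TTP analysis | Kaplan-Meier, quartiles, 95% CIs, curve | none |
| Recorded reason for change | – | none (1.5, 1.6) |

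Descriptive statistics in SAP 2.4.4.2 cannot be read as including Kaplan-Meier, because the same list names Kaplan-Meier separately for OS and PFS. The summary covers all patients who respond, so a censored responder enters at the censored time. The SAP does not name the statistics. Its only general list is in 2.4.1, under baseline characteristics: "Continuous data will be summarized using the number of available data, mean, standard deviation, median, minimum, and maximum for each treatment group". Applying that list to DOR is an inference. It contains no quartiles and no intervals.

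**Size (illustration)**

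The documents give no DOR figure for this trial to reproduce.

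Inputs from the documents:
- Responders: 28% of 33 = 9.24, so 9 (protocol 13.1).
- Cutoffs after the last patient's first dose: 4 and 20 months (protocol 6.7.2), and about 12 months for the second lock (SAP 4).
- Upper bound on accrual: first enrolment was in September 2016 (Phase 1 SAP 1.6). Cohort 2 could open no earlier than 7 + 28 = 35 days later (protocol 6.2.2), so early October 2016. The first analysis, with its cutoff 4 months after the last first dose, had been done by 14 December 2018 (Appendix J, Amendment 04). The last first dose was therefore no later than about mid-August 2018, which gives about 22 months. This takes the Cohort 2 dose as the recommended dose.

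Assumptions not in the documents: exponential DOR with true median m = 8 or 12 months; response at 1–3 months, uniform; uniform accrual over A = 6 to 22 months.

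*Mean.* With λ = ln 2 / m, the true mean is 1/λ = 11.5 months (m = 8) or 17.3 months (m = 12). A responder's censoring time is C = A + c − entry − time to response, where c is the cutoff. For exponential T, E[min(T, C)] = (1/λ) × (1 − P(censored)), so the proportional shortfall of the plain mean equals the censored share:

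P(censored) = e^(−λ(A+c)) × (e^(λA) − 1)/(λA) × (e^(3λ) − e^λ)/(2λ)

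For m = 8, A = 6, c = 20: 0.1051 × 1.3115 × 1.1907 = 0.164. The plain mean is 11.54 × (1 − 0.164) = 9.65 months, 16% short. For c = 4, e^(−10λ) = 0.4204 replaces 0.1051 and the censored share is 0.66.

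*Median.* At 20 months every C is at least 20 − 3 = 17 months, beyond both true medians, so censoring does not disturb the median. At 12 months the smallest C is 9 months, above 8 but below 12. At 4 months it is 1 month.

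Simulation with 9 responders, 20,000 trials per scenario (ranges over accrual length; longer accrual gives the smaller effects):

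| Cutoff | Plain median, true 8 | Mean short, true 8 | Plain median, true 12 | Mean short, true 12 |
|---|---|---|---|---|
| 20 months | 8.5–8.6 | 9–16% | 12.3–12.5 | 20–30% |
| 12 months | 7.9–8.2 | 19–33% | 9.8–11.1 | 32–48% |
| 4 months | 3.9–6.1 | 38–66% | 4.2–7.6 | 50–75% |

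With 9 fully observed responders the sample median averages 8.6 and 12.9, so values slightly above 8 and 12 are small-sample behaviour. At 4 months Kaplan-Meier would report the median as not reached in about 8–60% (true 8) and 23–78% (true 12) of trials. With assessments on a 28-day grid, the 4-month plain medians are 3.7–6.2 and 3.9–7.6, and the 20-month mean is 6–14% and 18–29% short.

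**The case against.** The strongest reply is that little changes where it counts. Protocol 6.7.2 says the "final analysis of time to events data will be 20 months after the date of the first dose of the last patient". At that cutoff the average Kaplan-Meier median (8.5–8.7 for a true 8; 11.7–12.8, when reached, for a true 12) differs from the plain median by about half a month or less. The protocol never planned a mean DOR. The 4-month cutoff is assigned to ORR, and with short accrual Kaplan-Meier does little better there, since the median is usually not reached. The SAP also asks to be read together with the protocol, so its silence on TTP is not a contradiction.

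Much of this stands. At 20 months the gain is mainly the intervals, the curve and the censoring counts. The mean is an inferred statistic. TTP adds little to PFS, which differs only in counting deaths; Appendix J mentions only two OS events in Phase II at the first analysis.

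Three points do not yield:
- The SAP does not say which lock reports DOR, and it puts the second one earlier than the protocol does: "The cut off for the second database lock is at approximately 12 months after last patient first dosed". That mismatch is a separate matter, but it means 20 months cannot be taken for granted from the SAP.
- One might say the SAP leaves the handling of censored responders open. But it summarises all responders, and excluding the censored ones would be worse: with assumed true medians of 6–18 months, the medians in those with events only were 2.1–9.3 months, always below the truth.
- Reading the SAP with the protocol does not settle DOR, where the two name different methods.

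**Conclusion.** The concern holds. The conflict over DOR and the omission of TTP are plain in the text, unrecorded and unexplained, and do not depend on any assumption. The numerical effect on DOR does. It is small for the median at 20 months and large for any plain summary at 4 months. For the mean, if one is reported, it equals the censored share under an exponential model. Those sizes are illustrative and rest on the assumed DOR distribution, accrual and response timing. The loss of DOR intervals and curve, and of any TTP result, applies at every cutoff. Both are untested secondary endpoints and the primary ORR test is unaffected, so this should be fixed but does not threaten the trial's main conclusion.

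**What to change.** In Phase 2 SAP 2.4.4.2, analyse DOR by Kaplan-Meier alongside OS and PFS: quartiles with 95% confidence intervals, the curve, and the numbers of events and censored responders. Keep descriptive statistics for TTR. Add TTP to 2.1.3.2 with the definition in protocol 9.3.1, and analyse it by Kaplan-Meier. State which database lock reports DOR and TTP. If the sponsor does intend to depart from the protocol on either endpoint, the SAP should say so and give the reason.

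The cost is SAP wording and two further Kaplan-Meier outputs from data already collected. With about 9 responders the intervals will be wide, and the median may not be reached at an early cutoff. Both convey the real uncertainty, which a plain summary would hide.

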#### **2.4.4.3 *Multiplicity issues***

Not applicable

#### **2.4.4.4 *Additional efficacy analysis(es)***

Not applicable

### **2.4.5 *Analyses of safety data***

All safety analyses will be performed on the safety population as defined in [Section 2.3.1](#), unless otherwise specified, the baseline value is defined as the last available value before the first isatuximab administration.

#### **2.4.5.1 *Analyses of adverse events***

##### ***Generalities***

The primary focus of adverse event reporting will be on treatment-emergent adverse events. Pre-treatment and post-treatment adverse events will be described separately.

If an adverse event date/time of onset (occurrence, worsening, or becoming serious) is incomplete, the adverse event will be classified as pre-treatment, treatment-emergent, or post-treatment, according to the cycle number or visit of onset. The algorithm for imputing date of onset will be conservative and will classify an AE as treatment emergent unless there is definitive information to determine it is pretreatment or post-treatment. Details on classification of adverse events with missing or partial onset dates are provided in [Section 2.5](#).

The grade will be taken into account in the summary. For patients with multiple occurrences of the same event during the observation period, the maximum grade is used.

Sorting within tables ensures the same presentation for the set of all adverse events within the observation period (pre-treatment, treatment-emergent, and post-treatment). For that purpose, the table of all treatment-emergent adverse events presented by SOC and PT sorted by the internationally agreed SOC order and decreasing frequency of PTs within SOCs will define the presentation order for all other tables unless otherwise specified.

The following treatment-emergent adverse event summaries will be generated for the safety population.

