9.1.2 Adverse Events

Safety profile will be based on incidence, severity (as graded by the NCI CTC AE v. 4.03), and cumulative nature of treatment-emergent AEs (TEAEs). TEAEs are defined as AEs that develop, worsen or became serious during the on-treatment period. For this study, the on-treatment period will be defined as the period from the time of first dose of IMP to at least 30 days after last administration of the IMP. Each patient will be assessed preferably by the same physician for AEs and according to the NCI CTC AE v. 4.03 classification.

Adverse events will be coded to “Preferred Term (PT)” and associated primary “System Organ Class (SOC)” using MedDRA (Medical Dictionary for Regulatory Activities). AEs will be summarized with respect to the type, frequency, severity, seriousness, and relatedness.

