13.4.4.2 Analyses of adverse events

Adverse events will be assessed according to NCI-CTCAE ver. 4.03 from the time of informed consent is signed until at least 30 days after the last IMP administration. AEs will be classified by System Organ Class/preferred term according to the latest available version of MedDRA dictionary.

Definitions

- Period of observation: The observation period will be divided into three segments: pre-treatment, on-treatment and post-treatment.
- The pre-treatment period is defined as the time from when the patients give informed consent to the start of IMP.
- The on-treatment period is defined as the time from the first dose of IMP up to 30 days after the last dose of IMP.
- The post-treatment period is defined as the time starting 31 days after the last dose of IMP to the study closure.

Pre-treatment AEs are defined as any AE during the pre-treatment period.

Treatment-emergent AEs (TEAEs) are defined as AEs that developed, worsened (according to the Investigator's opinion) or became serious during the on-treatment phase.

Post-treatment AEs are defined as AEs that are reported during the post-treatment period.

The grade and cycle will be taken into account in the summary. For patients with multiple occurrences of the same PT, the maximum grade is used. The denominator used for the summary by cycle is the total number of cycles administered in dose level. For a given PT, a patient contributes 1 to the numerator for each cycle in which an episode occurred.

The primary focus of AE reporting will be on TEAEs. Pre- and post-treatment AEs will be described separately.

Adverse event incidence tables will present for each dose level, the number (n) and percentage (%) of patients experiencing an AE. Multiple occurrences of the same event in the same patient will be counted only once in the tables within a treatment phase. The denominator for computation of percentages is the number of patients in the all treated population.

The table of all TEAEs presented by system organ class (SOC) and preferred terms (PT) sorted by internationally agreed order in SOC and descending order of that frequency in the pooled dose in PT (in case of the same frequency, then alphabet order) unless otherwise specified.

The following TEAE summaries will be generated:

Overview of TEAEs, summarizing number (%) of patients with any

- TEAEs
- Any Grade 3-4 TEAEs
- Drug-related TEAEs
- Drug-related TEAEs of Grade 3-4
- Serious TEAEs

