## **1.6 STATISTICAL MODIFICATIONS MADE IN THE STATISTICAL ANALYSIS PLAN**

Not applicable as this is the 1st version of the SAP.

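### Both SAPs drop the protocol's by-cycle adverse-event frequency without recording it, so general TEAE tables show neither recurrence nor timing

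*SAP*

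**What the plan says.** Protocol 13.4.4.2, on adverse events: "The grade and cycle will be taken into account in the summary". It then gives the denominator, "The denominator used for the summary by cycle is the total number of cycles administered in dose level", and the numerator, "For a given PT, a patient contributes 1 to the numerator for each cycle in which an episode occurred".

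Protocol 9.1.2 (and 9.1 in similar terms): "Safety profile will be based on incidence, severity (as graded by the NCI CTC AE v. 4.03), and cumulative nature of treatment-emergent AEs (TEAEs".

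Phase 1 SAP 2.4.5.1 and Phase 2 SAP 2.4.5.1 use the same words, under Generalities: "The grade will be taken into account in the summary", followed by "For patients with multiple occurrences of the same event during the observation period, the maximum grade is used". Neither gives a by-cycle numerator or denominator for adverse events.

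On changes, Table 1 of each SAP (protocol amendments) has one adverse-event entry, about the TEAE overview. Table 2 of the Phase 1 SAP lists five changes, and the only one on adverse events concerns infusion associated reactions. Phase 2 SAP 1.6 reads "Not applicable as this is the 1st version of the SAP".

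**The concern.** The current protocol fixes a safety analysis with its counting rules, and the two plans that will be programmed leave it out without comment. Whoever follows the SAPs will not produce it, and the reader of the report will not know that it was planned.

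The omission has a practical effect. Treatment is weekly in Cycle 1, then every 2 weeks until progression or another reason to stop, so patients contribute very different numbers of cycles. A table with one worst grade per patient over the whole on-treatment period counts a single episode and an event that returns in every cycle in the same way. Protocol 6.2, 6.3 and 9.1.1 also say that cumulative toxicity after Cycle 1 should be weighed in dose-selection decisions, so recurrence matters to this protocol.

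**Working it through.** No sample size, power or alpha figure is involved, so there is no plan figure to reproduce. The check is a comparison of texts followed by an illustration.

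**Step 1: the texts side by side**

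| Element | Protocol 13.4.4.2 | Phase 1 and Phase 2 SAP 2.4.5.1 |
|---|---|---|
| What the summary reflects | grade and cycle | grade only |
| Multiple occurrences | maximum grade | maximum grade over the observation period |
| By-cycle numerator | 1 per patient per cycle with an episode, for each PT | absent |
| By-cycle denominator | all cycles administered at the dose level | absent |

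**Step 2: what the SAPs keep**

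- Both analyse infusion associated reactions by patient, infusion and episode, including day of onset.
- Both tabulate TEAEs starting within 24 hours of an infusion (Phase 1 and Phase 2 SAP 2.1.4.1).
- Phase 1 tabulates DLTs, which belong to Cycle 1, and lists all adverse events.
- Phase 2 analyses late respiratory events within the post-treatment events. Its section 2.4.5.1 names listings for particular classes of event but none of all adverse events.
- Every other TEAE table counts patients, with no breakdown by cycle, onset time or recurrence.

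**Step 3: illustration of what is lost**

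Inputs: N = 33 patients (the lower end of the 33-36 in protocol 13.1). Assumed: C = 6 cycles each and k = 9 patients with a given PT. Cycles administered: 33 × 6 = 198.

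- SAP rule: k/N = 9/33 = 27.3%, whatever the pattern.
- Protocol rule: (patient-cycles with an episode)/(N × C).
  - One episode per affected patient: 9/198 = 4.5%.
  - An episode in all 6 cycles for the same 9 patients: (9 × 6)/198 = 54/198 = 27.3%.

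The contrast depends on C. With the same 9 of 33 patients, a single episode each gives 9/66 = 13.6% at C = 2 and 9/396 = 2.3% at C = 12. Recurrence in every cycle gives 27.3% at any C.

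**Step 4: what the protocol rule cannot show**

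| Pattern (9 affected, C = 6) | SAP rule | Protocol rule, pooled | Cycle 1 only (33 cycles) | Cycles ≥2 (33 × 5 = 165 cycles) |
|---|---|---|---|---|
| Once each, all in Cycle 1 | 27.3% | 9/198 = 4.5% | 9/33 = 27.3% | 0/165 = 0% |
| Once each, all in Cycle 6 | 27.3% | 9/198 = 4.5% | 0/33 = 0% | 9/165 = 5.5% |
| Every cycle | 27.3% | 54/198 = 27.3% | 9/33 = 27.3% | 45/165 = 27.3% |

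The pooled rule separates recurrence from single episodes, but the first two rows look the same under it. Only the split by cycle band, which the protocol does not ask for, separates early from late events.

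**Step 5: cycle boundaries**

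Protocol 13.4.4.4 (laboratory data) and Phase 1 SAP 2.5.4 place the first day of a cycle in that cycle. Phase 2 SAP 2.5.4 reverses this: the first day of a cycle is excluded and the first day of the next is included. All three are worded for sampling dates. Applied to adverse events, the Phase 2 rule would put Day 1 infusion-day events in the preceding cycle and Cycle 1 Day 1 events in no cycle.

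**The case against.** The strongest reply has four parts.

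- **The protocol's named tables are also patient-level.** Section 13.4.4.2 goes on to say that repeated events count once per patient within a treatment phase, and neither its table list nor the synopsis names a by-cycle AE table. This makes the by-cycle count look like a convention without an output. It is still mandatory wording with its own numerator and denominator, whereas the laboratory section allows a choice between patient and cycle.
- **The link to cumulative toxicity is an inference.** A reader might conclude that by dropping the summary the SAPs leave cumulative toxicity unanalysed. The documents do not support that. Sections 9.1 and 9.1.2 do not refer to the by-cycle count, the pooled rule measures recurrence and not a trend with exposure, and the analyses in Step 2 remain. This objection stands. What survives is that general TEAE summaries carry no information on recurrence or timing.
- **Timing was never in the protocol rule.** A reader might blame the SAPs for losing the contrast between Cycle 1 and later cycles. Step 4 shows that the pooled rule never gave it, so the split proposed below is an addition.
- **The change records cover major changes only.** Sections 1.5 and 1.6 say so, and the Phase 2 entry describes version history; it does not claim full conformity with the protocol. So the records are not shown to be false. They simply give no reason for a conflict with the current protocol.

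**Conclusion.** The point holds as a minor one. Both SAPs omit a by-cycle adverse-event frequency that protocol 13.4.4.2 specifies, and neither records or justifies this. Apart from the infusion-reaction and within-24-hour analyses, Phase 1 DLTs and late respiratory events, no planned TEAE summary shows recurrence or timing.

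In the illustration, two patterns that the protocol rule reports as 4.5% and 27.3% both appear as 27.3% under the SAPs. This rests on assumed figures (6 cycles for every patient, 9 affected) and on counting an episode in each cycle in which it occurs. Real exposure will be uneven, so the size of the contrast will differ.

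This is descriptive safety reporting. It does not affect the primary ORR analysis and involves no clinical-management rule.

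**What to change.** In section 2.4.5.1 of both SAPs:

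1. Reinstate the protocol's by-cycle TEAE summary by PT, for all grades and Grade ≥3, over cycles administered at the dose level.
2. As an addition beyond the protocol text, show it separately for Cycle 1 and Cycles ≥2, with the cycles and the patients started in each band as denominators.
3. State how an event that continues across cycles is counted, which the protocol leaves open. If it counts in each cycle it touches, onset dates alone are not enough, and a rule for missing end dates is needed because SAP 2.5.3 does not impute them.
4. Assign Day 1 of a cycle to that cycle, as in protocol 13.4.4.4 and Phase 1 SAP 2.5.4, and correct the reversed boundary in Phase 2 SAP 2.5.4.

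If the sponsor prefers to leave the summary out, the departure and its reason should be recorded in SAP 1.5 or 1.6.

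The cost is one or two extra descriptive tables from event and dosing dates already collected.
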